### 6.2.1. Description of the planned statistical methods, including the timing of planned interim analyses

All variables will be described globally and by group. The description will include the numbers and percentages of modalities for qualitative variables and the minimum, maximum, mean, standard deviation and median for quantitative variables.

### VAS pain

The average pain felt during the procedure (collected 5 minutes after the procedure) will be estimated with a 95% confidence interval in the two groups. It will be compared using a Student's t test.

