## **4. DESIGN AND STUDY PROCESS**

### ***4.1. GENERAL RESEARCH METHODOLOGY***

The research has the following characteristics:

- Type of research: Minimal Risk Minimal Constraint Interventional Research (MRIC) - Single-centre, controlled, randomised, open-label, superiority study.

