#### **Hypnosis-guided echo infiltration technique - Experimental arm:**

Hypnosis will be started after the result of the randomisation, the patient will be taken care of by the nurse trained in hypnosis (see § 4.4 description of the method used).

When the patient is ready, just after the hypnosis session, the nurse will disinfect the patient's hand in 3 steps with an iodinated skin antiseptic and the rheumatologist will perform the infiltration in a standardised way.

In both groups, the Spielberger Anxiety-Trait Scale (STAI form Y-B) will be collected before the intervention and before hypnosis (experimental arm). This score will be used to characterise and describe patients' anxiety before the intervention.

In both groups, the Spielberger Anxiety-Status Scale (STAI form Y-A) will be performed 5 minutes after the infiltration procedure.

The pain VAS will be collected before the hypnosis intervention in order to characterise the pain related to the pathology.

[figure not shown]
The pain VAS will then be collected 5 minutes after the infiltration procedure in order to characterise the pain linked to the infiltration procedure.

The use of analgesic treatments by the patient before the ultrasound guided infiltration will be collected.

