## TIMETABLE OF THE STUDY

Actions	J0 (Inclusion visit)	5 minutes after the action
Patient information	X	
Informed oral consent	X	
Randomisation	X	
Background	X	
Clinical examination	X	
Hypnosis	X	
Medical procedures: ultrasound-guided infiltration	X	
VAS for pathology-related pain	X	
EVA pain of the gesture		X
Anxiety-Trait Scale	X	
Anxiety-Status Scale		X
Analgesic treatments	X	

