#### **4.6. IDENTIFICATION OF ALL SOURCE DATA NOT IN THE MEDICAL RECORD**

- EVA pain before the infiltration procedure and before hypnosis
- VAS pain 5 minutes after the infiltration procedure
- Anxiety-Treatment scale before the infiltration procedure and before hypnosis
- Anxiety-Status scale 5 minutes after the infiltration procedure

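### Optional improvement: the unadjusted primary t test is valid, but the pre-procedure pain VAS has no role in it; adjusting costs at most about 0.6 power points and gains power only if the correlation exceeds about 0.12

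*Combined protocol and SAP*

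**What the plan says.** Section 6.2.1 (VAS pain) plans a mean with a 95% confidence interval in each group and one comparison: "It will be compared using a Student's t test". No covariate is named. Section 6.2.8 sets unstratified 1:1 randomisation in blocks.

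A pain VAS is also taken earlier. Section 4.2 says "The pain VAS will be collected before the hypnosis intervention in order to characterise the pain related to the pathology", and then "The pain VAS will then be collected 5 minutes after the infiltration procedure in order to characterise the pain linked to the infiltration procedure". The timetable lists them as "VAS for pathology-related pain" (inclusion visit) and "EVA pain of the gesture" (5 minutes after). Section 4.6 lists "EVA pain before the infiltration procedure and before hypnosis" among the source data.

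In section 6.2 the earlier reading is covered only by the general statement "All variables will be described globally and by group". Section 6.2.5 plans multiple imputation for the primary outcome but does not list the variables in the imputation model.

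On timing, section 4.2 puts randomisation in the inclusion consultation and the first VAS before hypnosis. It does not say whether that VAS comes before or after the allocation is known. Section 4.1 describes a "Single-centre, controlled, randomised, open-label, superiority study".

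**The concern.** A baseline measure of the same kind as the outcome is often its best available predictor. When it is collected anyway, leaving it out can give up precision that would need no extra patients. If the pre-procedure VAS predicts the 5-minute VAS, adjustment removes that part of the residual variance and narrows the interval for the treatment difference.

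Two further points bear on the choice. First, it has to be made before the data are seen; choosing between adjusted and unadjusted results afterwards would be data-driven. Second, a baseline covariate must not be affected by the arm. If patients or nurses know the allocation when the first VAS is taken, an arm-dependent shift of size d in that reading moves the adjusted treatment difference by the regression slope times d. The planned t test does not use the first VAS, so it is not exposed to this.

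**Working it through.** **Inputs.** From section 6.2.2: difference 2 points, SD 3, power 80%, 74 patients required, 80 to be randomised. From section 6.2.3: alpha 5%. From section 6.2.8: 1:1 allocation. Sidedness is not stated; two-sided is assumed because it reproduces 74 (one-sided, by the normal approximation, gives 56). The correlation r between the two VAS readings is not in the documents; 0 to 0.5 is an assumed range.

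**Step 1: the plan's own figure.** For a two-sided t test with N patients, the standard error is 3 × √(4/N), the noncentrality is 2 divided by that, and there are N − 2 degrees of freedom.
- N = 72: power 79.7%.
- N = 74: SE = 3 × √(4/74) = 0.697, noncentrality 2.87, power 80.76%. So 74 is the smallest even total reaching 80%, as the plan states.
- N = 80: SE = 3 × √(4/80) = 0.671, noncentrality 2.98, power 83.76%. The 95% CI half-width for the difference is 1.336.

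**Step 2: the adjusted analysis.** With one covariate:
- the residual SD becomes 3 × √(1 − r²);
- there are N − 3 degrees of freedom;
- chance baseline imbalance multiplies the variance by 1 + F/(N − 2), with F distributed as F(1, N − 2). Power is averaged over F.

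| r (assumed) | Power, N = 80 | Change from 83.76% | Half-width, N = 80 | Power, N = 74 | Change from 80.76% |
|---|---|---|---|---|---|
| 0 | 83.27% | −0.49 | 1.344 | 80.20% | −0.56 |
| 0.1 | 83.64% | −0.12 | 1.338 | 80.59% | −0.17 |
| 0.2 | 84.74% | +0.98 | 1.317 | 81.77% | +1.01 |
| 0.3 | 86.57% | +2.81 | 1.283 | 83.75% | +2.99 |
| 0.4 | 89.09% | +5.33 | 1.232 | 86.53% | +5.77 |
| 0.5 | 92.18% | +8.42 | 1.164 | 90.02% | +9.26 |

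**Step 3: break-even.** The mean of F is (N − 2)/(N − 4), so the average variance factor is 1 + 1/(N − 4). Setting (1 − r²) × (1 + 1/(N − 4)) = 1 gives r = √(1/(N − 3)): √(1/77) = 0.114 for N = 80 and √(1/71) = 0.119 for N = 74. Solving on power itself gives 0.115 and 0.120.

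**Step 4: worst case.** At r = 0, scanning true differences from 0.3 to 3.45, the largest loss is 0.57 points with 80 patients (at a difference of 1.65) and 0.62 with 74 (at 1.70). Nearly all of it comes from chance imbalance; at a difference of 2, the lost degree of freedom alone costs 0.01 to 0.02 points.

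**Step 5: a smaller effect.** At 1.1 points, the decrease that section 6.2.2 cites as clinically significant in rheumatoid arthritis, the t test with 80 patients has 36.70% power. Adjustment gives 36.30%, 37.55%, 39.25% and 45.94% at r = 0, 0.2, 0.3 and 0.5: changes of −0.40, +0.85, +2.55 and +9.24 points.

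**Step 6: simulation.** With normal outcomes, N = 80 and 200,000 trials per setting, t test against adjusted power was 83.7% and 83.3% (r = 0), 83.9% and 83.9% (0.12), 83.7% and 86.6% (0.3), and 83.8% and 92.1% (0.5). A separate run of 40,000 trials per setting gave type I error of 4.9 to 5.1% for both methods. With values clipped to the 0–10 scale (assumed means and spread, 20,000 trials per setting), power was 82.4% and 81.8% (r = 0), 82.3% and 85.1% (0.3), and 82.7% and 90.8% (0.5), with type I error of 4.9 to 5.2%.

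**The case against.** The strongest objection is that nothing is broken. An unadjusted t test under unstratified 1:1 randomisation is a legitimate prespecified choice and meets the power target. That stands, and it is why this is only an improvement to consider.

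The second is that every gain depends on a correlation the documents do not give, and what they do say points low: the first reading is meant to capture the disease and the second the procedure. This also stands. At r of 0.2 or less the gain is about 1 point at most and the half-width falls by only about 0.02 (1.336 to 1.317), which would rarely change a conclusion. The rows for r = 0.4 and 0.5 show what is possible, not what is expected.

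Third, the order of collection becomes a problem for the primary comparison only if adjustment is adopted. That is correct, and the recommendation is conditional for this reason.

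Lesser points:
- The plan promises an interval in each group, not one for the difference, so the half-widths above are for an interval that would have to be added.
- The first VAS may be intended for the imputation model. That would still not make it a covariate in the comparison.
- The 1.1-point case is not the design difference and is shown only for sensitivity.
- Section 4.2 says both groups for the anxiety scales but not for the first VAS. The timetable and section 4.6 do not restrict it by arm, so no new measurement should be needed, but the wording should be made explicit.

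**Conclusion.** The point holds as an optional improvement. The t test is unbiased, has correct type I error, and gives 83.8% power at 80 patients (80.8% if 74 are analysed). Prespecified adjustment for the pre-procedure VAS risks at most about 0.6 power points and breaks even at a correlation of about 0.12. With 80 patients it would gain about 1 point at r = 0.2, 2.8 at 0.3 and 8.4 at 0.5.

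These figures assume a two-sided test, SD 3, a difference of 2 unless stated otherwise, and normal outcomes with a common SD; the check on a clipped scale gives the same pattern. The downside is bounded and known. The upside depends on an unknown correlation and may well be small. Confidence that the change is worthwhile is therefore moderate.

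**What to change.** 1. In section 4.2 and the timetable, state that the baseline pain VAS is recorded in both arms before the randomisation result is obtained.
2. On that condition, replace the primary comparison in section 6.2.1 with a linear model of the 5-minute VAS on arm and baseline VAS only. Report the adjusted mean difference with its 95% confidence interval.
3. In section 6.2.5, include arm and baseline VAS in the imputation model, fit the primary model in each imputed dataset, and pool the results.
4. Keep the unadjusted t test as a sensitivity analysis.
5. If the order in item 1 cannot be guaranteed, keep the t test as primary.

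The cost is one degree of freedom (77 instead of 78 at 80 patients), at most about 0.6 power points if the baseline VAS predicts nothing, and a fixed order at the inclusion visit. No new measurement or staff should be needed. Because the primary analysis and the order of procedures would change, an amendment step under section 7.6 may be needed. The decision should be made before outcome data are seen.

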### Anxiety

Anxiety after the procedure will be collected using the State-Anxiety questionnaire (STAI form YA). The total score of the questionnaire will be calculated in both groups. The mean will be presented with a 95% confidence interval and compared using a Student's t test.

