## **2.2. OBJECTIVES AND SECONDARY ENDPOINTS**

### **2.2.1. Secondary objective(s)**

Assessment of patient anxiety 5 minutes after the procedure is performed

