### ***4.2. CONDUCT OF THE STUDY AND TIMETABLE OF THE STUDY***

#### **1. Inclusion and Randomisation (D0)**

oIn order to ensure the feasibility of the study, patients scheduled for ultrasound-guided hand infiltration will be scheduled when two nurses, one of whom is trained in hypnosis, are present on the ward.

The inclusion consultation will check the inclusion and non-inclusion criteria. A presentation of the study will be made by one of the two nurses. Written information will be given to the eligible patient. The patient's oral, informed consent will then be collected.

Randomisation will be carried out during this consultation. Depending on the randomisation arm the patient will receive either :

- A single ultrasound-guided infiltration of the hand (standard arm)
- A single ultrasound-guided infiltration of the hand under hypnosis (experimental arm).

In this study, where the standard of care is "infiltration only", a placebo group is not planned. The aim of our study is to evaluate the contribution of hypnosis as a global approach to patient management.

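### The only secondary endpoint (STAI Y-A) is compared without adjustment although trait anxiety (Y-B) is already collected; prespecifying Y-B as a covariate may narrow the confidence interval at little cost

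*Combined protocol and SAP*

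**What the plan says.** Section 2.2 has one secondary objective, "Assessment of patient anxiety 5 minutes after the procedure is performed", and one matching endpoint, the STAI Y-A score. Its analysis is in section 6.2.1, under Anxiety: "The mean will be presented with a 95% confidence interval and compared using a Student's t test". No covariate-adjusted analysis appears anywhere in section 6.2.

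Trait anxiety is described in section 4.2, at the end of the experimental-arm text: "In both groups, the Spielberger Anxiety-Trait Scale (STAI form Y-B) will be collected before the intervention and before hypnosis (experimental arm"). Its only stated purpose follows: "This score will be used to characterise and describe patients' anxiety before the intervention". State anxiety is not measured before the procedure, so Y-B is the only pre-procedure anxiety score.

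On the order of events, section 4.1 describes a "Single-centre, controlled, randomised, open-label, superiority study". Section 4.2 says of the inclusion visit that "Randomisation will be carried out during this consultation", and of the experimental arm that "Hypnosis will be started after the result of the randomisation". The timetable puts randomisation and the "Anxiety-Trait Scale" in the same J0 column without ordering them. Section 6.2.5 provides multiple imputation for the primary outcome only.

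**The concern.** Patients complete a 20-item anxiety questionnaire before the procedure, and the comparison of their anxiety afterwards makes no use of it. If usual anxiety predicts anxiety after the injection, adjusting for it removes some of the between-patient variation and narrows the interval for the arm difference without extra patients. The trial is sized on pain alone, so precision on Y-A is whatever the 80 patients provide. The covariate has to be named in advance, because an adjustment chosen after the data are seen is open to selection.

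Two details decide whether the adjustment would be sound.

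- **Timing.** Placing Y-B before hypnosis, when hypnosis itself follows the randomisation result, allows the form to be completed once the patient knows the arm. A self-report given then might not be a clean baseline.
- **Missing Y-B.** With no rule, a patient who has Y-A but no Y-B stays in the t test and drops out of the adjusted model.

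**Working it through.** **The plan's own figure.** Section 6.2.2 gives a 2-point difference in pain VAS, SD 3, alpha 5% and power 80%. Sidedness is not stated; two-sided is assumed. The normal approximation gives n = 2(1.960 + 0.842)² × 3²/2² = 35.3, so 36 per arm. The noncentral t gives power 79.7% at 36 and 80.8% at 37 per arm, hence 74 in total, as stated. Adding 5% gives about 78; the plan says 80. No SD, effect or power is given for Y-A, so the rest is in SD units of Y-A.

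**Inputs.** 80 patients, 1:1 (sections 6.2.2 and 6.2.8), so 40 per arm. The within-arm correlation r between Y-B and Y-A is not in the documents; r = 0 to 0.5 is assumed.

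**Unadjusted t test.** SE = √(2/40) = 0.2236, 78 df, t = 1.9908, half-width 0.2236 × 1.9908 = 0.445.

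**Adjusted model.** The SE is multiplied by √[(1 − r²)(1 + 1/76)], where 1/76 = 1/(N − 4) is the expected price of estimating the covariate effect; 77 df, t = 1.9913. Equivalent N = 80/[(1 − r²)(1 + 1/76)]. The last column comes from simulating 20,000 trials at each r.

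| r (assumed) | Half-width | Change in CI width | Equivalent N | Trials in which the adjusted CI is wider |
|---|---|---|---|---|
| 0 | 0.448 | +0.7% | 79.0 | 80% |
| 0.1 | 0.446 | +0.2% | 79.8 | 65% |
| 0.2 | 0.439 | −1.4% | 82.3 | 34% |
| 0.3 | 0.428 | −4.0% | 86.8 | 11% |
| 0.4 | 0.411 | −7.7% | 94.0 | 2% |
| 0.5 | 0.388 | −12.8% | 105.3 | 0.2% |

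In the simulation, type I error was 4.8% to 5.3% for both analyses.

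**Break-even.** On the SE, (1 − r²)(77/76) = 1 gives r² = 1/77, r = 0.114. On the CI half-width, with the lost degree of freedom, r = 0.116.

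**Cost on two scales at r = 0.** Variance: 1 + 1/76 = 1.013, or 1.3%. CI width: √1.0132 × 1.9913/1.9908 = 1.0068, or 0.7%.

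**With 74 evaluable patients.** The r = 0 cost is 0.7%, and the gains at r = 0.2 to 0.5 are 1.3%, 3.9%, 7.7% and 12.8%.

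**If patients with a missing Y-B are dropped.** With m dropped, as evenly as possible across arms, the adjusted half-width is √(1/n₁ + 1/n₂) × √[(1 − r²)(1 + 1/(76 − m))] × t on 77 − m df. This is compared with 0.445 from the t test on all 80.

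| Dropped | Change in CI width at r = 0 | Break-even r |
|---|---|---|
| 0 | +0.7% | 0.12 |
| 1 | +1.3% | 0.16 |
| 2 | +2.0% | 0.20 |
| 4 | +3.4% | 0.25 |

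Four of 80 is 5%, an assumption of the same size as the addition in section 6.2.2.

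**The case against.** An unadjusted comparison in a 1:1 randomised trial is legitimate, the endpoint is secondary, and the documents promise no precision for it. All of that stands, and it keeps this a low-severity point. A reader might infer that the t test is biased or its alpha wrong; nothing in the documents supports that.

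The benefit rests on an unknown correlation. Section 4.5 describes two different constructs, feeling at this moment and feeling usually, and nothing in the documents shows that r exceeds break-even. At r = 0.2 the adjusted interval is still the wider one in about a third of trials. So adjustment may help; it is not bound to.

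A reader might also take the cost as under 1% without qualification. That holds for CI width or SE with complete Y-B. It does not hold for variance, nor once a single patient is dropped for a missing Y-B. This is why a missing-score rule belongs in the proposal.

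On timing, a reader might infer that Y-B is contaminated by knowledge of the arm. The documents show only that the order is not fixed. Y-B asks how the patient feels in general, so it should be less exposed than a state measure, and under the current plan it is descriptive only. The order matters mainly once Y-B becomes a covariate.

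Finally, section 6.2.1 also compares pain VAS without adjustment, although a pain VAS is collected before the procedure. Adjusting only the secondary endpoint would look uneven, and the sponsor may prefer one decision for both. That does not weaken the case for Y-A.

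**Conclusion.** The point holds as an optional gain in efficiency, to be considered. With 80 patients and complete Y-B, the expected loss in CI width is at most 0.7%, against a gain of 4.0% to 12.8% if r lies between 0.3 and 0.5; break-even is near 0.12. These figures assume a linear relation with the same slope in both arms, 40 patients per arm, and a range of r that the documents neither support nor exclude. The low cost also depends on not dropping patients for a missing Y-B, and the soundness of the adjustment on Y-B being completed before the allocation is known. The sample size and the primary pain conclusion do not change.

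**What to change.** - **Section 6.2.1, Anxiety.** Prespecify a linear model of post-procedure Y-A on arm and Y-B, and report the adjusted between-arm difference with its 95% CI. Keep the Student's t test as a supporting analysis.
- **Section 6.2.1 or 6.2.5.** Replace a missing Y-B by a simple rule that ignores arm, for example the overall mean of the observed Y-B scores, so that no patient with a Y-A score is dropped.
- **Section 4.2 and the timetable.** State that Y-B is completed before the allocation is known.

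The cost is a few sentences and a fixed order for two steps already done at the same visit. It needs no new patients, data or questionnaires. If Y-B proves unrelated to Y-A, the price is about one patient's worth of information.

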### 6.2.2. Statistical justification of the number of inclusions

Currently, there is no data in the literature on the pain experience during ultrasound-guided infiltration of the hand. It has been shown that a decrease of 1.1 on the VAS is clinically significant in patients with rheumatoid arthritis (Wolfe et al. 2007).

We hypothesise that the hypnosis session may reduce the pain experienced during the procedure by 2 points. According to data from a study carried out in the department on patients for whom an infiltration of the thumb is indicated, we have retained a standard deviation of 3 for the pain felt during the infiltration procedure. Based on these assumptions and setting an alpha risk of 5% and

a power of 80%, a total of 74 patients should be randomised. In order to guarantee the power of the study, an additional 5% of patients will be randomised, i.e. 80 patients in total.

### **6.2.3. Expected level of statistical significance**

The alpha risk is set at 5%.

### **6.2.4. Statistical criteria for stopping the research**

NA

### **6.2.5. Method of accounting for missing, unused or invalid data**

All missing data and the reason for it will be described in each group.

For the analysis of the primary outcome, a multiple imputation method will be applied.

### **6.2.6. Managing changes to the original strategy analysis plan**

NA

### **6.2.7. Selection of persons to be included in the analyses**

The main analysis will be performed on the Intent-to-Treat (ITT) population, i.e. on all randomised patients.

A complementary analysis will be performed on the Per Protocol (PP) population including the randomised patients for whom no major protocol deviations have been identified.

A data review meeting will be held to review and define the major criterion or not for each of the deviations.

### **6.2.8. Randomisation**

Randomisation will not be stratified.

It will be carried out in a 1:1 ratio and will be done in blocks.

Randomisation will be carried out in Ennov Clinical by connecting to the website: <https://www.dirc-hugo-online.org/csonline/>. The connection will be made through a login, a password and a study number, delivered by the data manager of the Research Unit of the La Roche sur Yon Hospital. The following information must be filled in:

- First initial of the name,
- First initial of the first name,
- Month and Year of birth,
- Compliance with inclusion and non-inclusion criteria (yes/no),

Randomisation will be carried out by the investigator after confirmation of the possibility of inclusion in the study. The inclusion number will be assigned automatically during randomisation. A confirmation email will be sent to the person who performed the randomisation and to all persons involved.

The randomisation list will be carried out by the statistician of the Research Unit of the CHD of La Roche sur Yon. An explanatory guide to randomisation will be available online in Ennov Clinical.

